7.6.3.2 Change from Baseline for Selected Laboratory Parameters

Scheduled laboratory measurements and corresponding change from baseline values will be summarized (mean baseline with standard deviation, mean post-baseline with standard deviation, mean change from baseline with standard error and 95% CI for change from baseline) by time point and laboratory test. For the Double-Blind Treatment Period (As-Treated Analysis Population) summaries will be provided by treatment group. For the cumulative abatacept period (cumulative abatacept population) all subjects' data will be combined into one treatment group.

Visit windows are provided in [Section 8.5](#) in order to link each laboratory test to a scheduled visit. The following laboratory parameters will be analyzed:

- Hemoglobin
- Hematocrit
- Total leukocyte
- Basophils
- Eosinophils
- Lymphocytes
- Monocytes
- Neutrophils
- Platelet count
- Aspartate aminotransferase (AST)
- Alanine aminotransferase (ALT)
- Total bilirubin
- Alkaline phosphatase
- Creatinine
- Blood Urea Nitrogen (BUN)
- Bicarbonate
- GGT (Gamma-glutamyltransferase)
- Glucose
- Total Protein
- Albumin
- Sodium
- Potassium
- Chloride
- Calcium
- Phosphorus
- Creatine kinase
- hsCRP
- Urine pH

Subjects who have laboratory measures at baseline and corresponding measure at the given on-treatment visit will be included in the laboratory analyte assessment. Note that not all subjects have laboratory determinations for all analytes at all visits, and therefore the sample size may vary from analyte to analyte at each time point. The 95% CI for the change from baseline within the treatment arm will be constructed based on t-test.

7.6.3.3 Pregnancy Test Results

A by-subject listing of positive pregnancy test results will be provided using the As-treated analysis population.

7.6.4 Vital Sign

Summaries of vital signs parameters (seated systolic blood pressure, seated diastolic blood pressure, heart rate, and body temperature) will be provided for each vital sign parameter at each timepoint. For the Double-Blind Treatment Period summaries (As-Treated Analysis Population) will be done by treatment group. For the cumulative abatacept period (cumulative abatacept population) all subjects' data will be combined into one treatment group. Visit windows are provided in [Section 8.5](#) in order to link vital sign assessment to a scheduled visit

7.6.5 Pharmacokinetic Analyses

PK Samples will be drawn to determine serum abatacept concentrations at Days 1, Week 4 (Day 29), Week 8 (Day 57), Week 12 (Day 85), Week 16 (Day 113), Week 20 (Day 141), and Week 24 (Day 169) in the Double-Blind Treatment Period, at Week 52 (Day 365) in the Open-Label Period. For subjects who discontinue during the Double-Blind Treatment Period samples drawn 85 and 169 days after their last dose of study medication will be evaluated to determine serum abatacept concentration in the event there is a corresponding positive immunogenicity result.

Trough serum concentration of abatacept will be summarized by study visits listed above for the Double-Blind and Open-Label Periods separately (PK evaluable population). Geometric means and coefficients of variation will be presented for C_{min} . Statistics that will be provided are N, Mean, Standard Deviation, Geometric Mean, %CV, Median, Minimum and Maximum.

7.7 Outcomes Research Analysis

The outcome research analysis endpoints described in this section for the Double-Blind Treatment Period are considered as secondary endpoints and exploratory in the open-label period.

The analysis for the below outcome research endpoints will follow the analysis methods for the continuous secondary efficacy endpoints detailed in [Section 7.5.2.1](#)

- Subject global assessment of disease activity (SubGDA) and physician global assessment of disease activity (phyGDA) will be analyzed separately (see [Section 8.1.9](#))
- Short Form - 36 (SF-36 v2.0) (see [Section 8.1.10](#)). Both the physical and mental scales as well as the individual sub-scales will be analyzed.
- Female Sexual Function Index (FSFI) (see [Section 8.1.11](#)). Both the full scale score and the individual domain scores will be analyzed.
- PROMIS Fatigue Short Form 8a (see [Section 8.1.12](#)).

The Numeric Rating Scale (NRS) scores for mouth and eye dryness (see [Section 8.1.8](#)) will be summarized by treatment and timepoint using descriptive statistics (median, interquartile range, minimum and maximum). Furthermore, all NRS scores available at baseline will be categorized based on tertiles (lowest third, middle third, and highest third). These same tertile cut points will be applied to all post-baseline data. The shift from baseline category to post-baseline category will be summarized at each post-baseline visit for each treatment group.

[REDACTED]

[REDACTED]

[REDACTED]

[REDACTED]

[REDACTED]

[REDACTED]

[REDACTED]

[REDACTED]

[REDACTED]

[REDACTED]

[REDACTED]

[REDACTED]

[REDACTED]

[REDACTED]

[REDACTED]

[REDACTED]

[REDACTED]

[REDACTED]

[REDACTED]

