- To assess the change from baseline in patient symptoms using the Numeric Rating Scale (NRS) for mouth dryness at all measured time points up to Day 169 in the full population, among those with stimulated whole salivary flow of at least 0.1mL/min at screening and baseline, and among those with stimulated whole salivary flow of less than 0.1mL/min at screening or baseline.
- To assess the mean change from baseline in patient symptoms using the Numeric Rating Scale (NRS) for eye dryness at all measured time points up to Day 169.
- To assess the mean change from baseline in patient symptoms using the patient global assessment of disease activity at all measured time points up to Day 169.
- To assess the mean change from baseline in the physician global assessment at all measured time points up to Day 169.
- To assess the mean change from baseline in patient fatigue using PROMIS Fatigue assessment at all measured time points up to Day 169.
- To assess the mean change from baseline in female sexual function using the Female Sexual Function Index (FSFI) at all measured time points up to Day 169.

- To assess the mean change from baseline in patient quality of life using the SF-36 (v2.0) at all measured time points up to Day 169.
- To assess safety and immunogenicity of abatacept.
- To assess the pharmacokinetics of abatacept.

[REDACTED]

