8.1.8 Numeric Rating Scale (NRS) Scores

The oral and ocular dryness are each assessed by the patients with numeric rating scales from 0 to 10 with 0 representing no dryness and 10 representing maximal dryness (protocol Appendices 8 and 9). The analysis will be based on the scores as reported on the CRF.

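### The SAP sets mean change in eye-dryness NRS as a secondary objective, but its visible NRS analysis gives no mean change

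*SAP*

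**What the plan says.** SAP 3.2 lists two dryness objectives among the other secondary objectives, both at all measured time points up to Day 169:

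- Eye dryness: "To assess the mean change from baseline in patient symptoms using the Numeric Rating Scale (NRS) for eye dryness".
- Mouth dryness: "To assess the change from baseline in patient symptoms using the Numeric Rating Scale (NRS) for mouth dryness", in the full population and in two salivary-flow subgroups.

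SAP 7.7 says that its double-blind endpoints "are considered as secondary endpoints and exploratory in the open-label period". It then splits them. For one group, "The analysis for the below outcome research endpoints will follow the analysis methods for the continuous secondary efficacy endpoints detailed in" 7.5.2.1; the bullets name the subject and physician global assessments, SF-36, FSFI and PROMIS Fatigue. The two NRS scales are not among them. A separate paragraph says that the NRS scores "will be summarized by treatment and timepoint using descriptive statistics (median, interquartile range, minimum and maximum". Baseline scores are also cut into thirds: "These same tertile cut points will be applied to all post-baseline data", and movement between categories is tabulated for each arm at each post-baseline visit.

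SAP 8.1.8 describes "numeric rating scales from 0 to 10 with 0 representing no dryness and 10 representing maximal dryness". Table 8.5-1 gives both scales the same visit windows as ESSDAI.

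**The concern.** The eye-dryness objective names a specific quantity, the mean change from baseline. The visible analysis gives the median, interquartile range and extremes of the scores at each visit, and a count of category shifts. No mean change can be read from these. SAP 7.7 gives no reason for leaving the NRS scales off the modelled list.

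At stake is whether the report can answer a stated secondary objective for a core symptom of the disease. ESSPRI fills the gap only in part. Its components are modelled under 7.5.2.1, but it has one combined dryness score and so cannot separate eyes from mouth.

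**Working it through.** The plan gives no figure to reproduce. The check compares the objective with the analysis, then asks how much change the shift table can show.

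**1. Objective against analysis**

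| Scale | SAP 3.2 objective | Visible SAP 7.7 analysis | Match |
|---|---|---|---|
| Eye dryness | Mean change from baseline | Median, IQR, minimum, maximum of scores; per-arm tertile shifts | No mean change |
| Mouth dryness | Change from baseline | The same | Change shown, but only as category shifts |

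**2. The listed statistics do not determine the mean change**

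An invented example, not trial data: three subjects score 5, 7 and 9 at baseline and 2, 7 and 8 later.

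- Median: 7 at both times.
- Mean change: (−3 + 0 − 1)/3 = −1.33.
- With assumed category limits of at most 5, 6 to 7, and above 7, each subject stays in the same category, so the shift table shows no movement.
- The minimum and maximum do move (5 to 2, 9 to 8), but they do not give the mean change.

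**3. Resolution of the shift table**

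Inputs: the 0 to 10 range (SAP 8.1.8), three categories with cut points fixed at baseline (SAP 7.7), and the assumption of whole-point scores. Let the lowest category be scores up to c1, the middle one scores up to c2, and the highest the rest, with 0 ≤ c1 < c2 ≤ 9.

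- A 1-point improvement from score s changes category only if s = c1 + 1 or s = c2 + 1. That is 2 of the 10 possible starting scores (1 to 10), whatever the cut points.
- A 2-point improvement crosses c1 from s = c1 + 1 or c1 + 2, and crosses c2 likewise. Over all pairs of cut points this gives 2 to 4 of the 9 possible starting scores (2 to 10).
- A subject in the lowest category at baseline has no lower category to enter, so cannot show improvement in this table. A subject in the highest category cannot show worsening.

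**4. Illustration on assumed inputs**

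The documents give no NRS distribution. Assume a normal baseline rounded to 0–10, with mean 5, 6 or 7 and cut points at the baseline tertiles. If every subject improved by 1 point, the share changing category would be 32% for an SD of 2, 27% for 2.5 and 24% for 3. Because of ties at whole scores, the lowest category would then hold 40% to 43% of subjects rather than a third.

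**5. Whether the data would support a model**

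Table 8.5-1 places both scales at Days 29, 57, 85, 113, 141 and 169. These are the six post-baseline double-blind visits used for ESSDAI.

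**The case against.** The strongest objection is redaction. The visible endpoint list in SAP 4.2 stops at unstimulated salivary flow. In the Protocol's order, the NRS endpoints come after stimulated flow, the next item. Parts of 7.5.2.1 are blacked out, as is the text after the NRS paragraph in 7.7. A hidden NRS model therefore cannot be excluded. This stands as a limit, but it does not undo the intact text of 7.7, which gives these scales their own descriptive rule outside the modelled list and points to no other analysis.

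A second objection is that medians and shifts are a legitimate choice for a single-item 0–10 scale, and that the score summaries cover every subject, including those in the lowest baseline category. That is fair. It defends the tables as description; it does not supply the mean change that the eye-dryness objective names.

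A reader might also infer more than the documents support:

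- **That mouth dryness is in the same direct conflict.** The SAP objective omits the word mean, and a shift table is a summary of change. Mean change for that scale comes from the supplied Protocol (8.3.2), whose visible history ends at Amendment 01, while the SAP also reflects amendments 6 and 8.
- **That SAP 8.1.8 rules out change scores** because it says "The analysis will be based on the scores as reported on the CRF". Section 8.1 deals with how measures are derived, and change from baseline is defined generally in 7.1.1.
- **That NRS is shown to be unmodelled** because 7.5.2.1 cites calculation sections 8.1.1 to 8.1.7 but not 8.1.8. The scales in 8.1.9 to 8.1.12 are not cited there either, yet 7.7 sends them to that model.
- **That the objectives promise a between-arm comparison.** SAP 3 speaks of comparing for the primary and key secondary objectives, and of assessing for the others. The absence of a treatment difference is not in itself a breach of the NRS objectives.
- **That the mouth-dryness flow-subgroup analysis is missing.** With the redactions, this cannot be said.

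**Conclusion.** The point holds in a narrow form and is minor. On the visible text, the eye-dryness NRS objective has no analysis that yields the mean change it names. The mouth-dryness objective is addressed, but only coarsely: the 2-in-10 figure needs only whole-point scores, and the lowest category cannot show improvement in the shift table. The 24% to 32% range rests on an assumed baseline distribution and is illustration only.

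No primary or key secondary conclusion depends on this. NRS is outside the hierarchical procedure, and SAP 7.5 plans no p-value for it. Confidence is limited by the redactions: the finding is that the visible plan does not match its objective, not that no NRS model exists anywhere.

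**What to change.** Add mouth- and eye-dryness NRS to the list in SAP 7.7 that is analysed under 7.5.2.1. At each visit to Day 169, report the adjusted mean change per arm and the treatment difference with its 95% CI, without a p-value, in line with SAP 7.5. Keep the median/IQR and tertile-shift tables as supportive. If a redacted section already models NRS, a cross-reference in 7.7 is enough. If a purely descriptive analysis is intended, 7.7 should say so and the eye-dryness wording in 3.2 should be aligned; that removes the mismatch but leaves mean change unreported.

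The cost is a short SAP edit and a few tables from the existing repeated measures program. No new data are needed, and the testing hierarchy is unchanged.

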7.10 Interim Analyses

No interim analysis is planned for this study.

8 CONVENTIONS

8.1 Calculations of Key Measures

8.1.1 *EULAR Sjögren's Syndrome Disease Activity Index (ESSDAI)*

The EULAR Sjögren's Syndrome Disease Activity Index (ESSDAI) total score is calculated as the sum of scores for activity level for each domain. The scores and the domains are presented in Table 8.1.1-1. If all components are missing, total ESSDAI score will not be calculated; otherwise missing component will be imputed to zero (since it is assumed that active domains are not likely to be left blank).

The ESSDAI domain scores will be calculated using the values presented in Table 8.1.1-1 for each domain separately.

Table 8.1.1-1: The EULAR Sjögren's Syndrome Disease Activity Index (ESSDAI) Scoring Algorithm

Domain	Score for activity level
Constitutional	No=0, Low=3, Moderate=6
Lymphadenopathy	No=0, Low=4, Moderate=8, High=12
Glandular	No=0, Low=2, Moderate=4
Articular	No=0, Low=2, Moderate=4, High=6
Cutaneous	No=0, Low=3, Moderate=6, High=9
Pulmonary	No=0, Low=5, Moderate=10, High=15
Renal	No=0, Low=5, Moderate=10, High=15
Muscular	No=0, Low=6, Moderate=12, High=18
Peripheral Nervous System (PNS)	No=0, Low=5, Moderate=10, High=15
Central Nervous System (CNS)	No=0, Moderate=10, High=15
Haematological	No=0, Low=2, Moderate=4, High=6
Biological	No=0, Low=1, Moderate=2

[REDACTED]

[REDACTED]

8.1.3 Salivary Flow Rate

Salivary flow rate is assessed as described in the protocol Section 5.4.2. The CRF collects information on start and stop date/time of saliva collection as well as the pre-collection and post collection weight of the tube used to collect saliva.

For analysis, the salivary flow rate will be expressed in ml per min (ml/min) using the formula below:

Figure 8.1.3-1: Formula for Calculating Salivary Flow Rate

$$\text{Salivary flow rate (ml/min)} = \frac{(\text{Post - collection weight in grams}) - (\text{Pre - collection weight in grams})}{(\text{Stop date/time of collection}) - (\text{Start date/time of collection}) \text{ in minutes}}$$

In the formula above, it is assumed that 1 gram of saliva corresponds to 1ml of saliva. Round to 2 decimals.

The same formula will be used for the calculation of both stimulated and unstimulated salivary flow rate.

8.1.4 DAS28-CRP

The disease activity score DAS28-CRP is a continuous variable which is a composite of 4 variables: the 28 tender joint count, the 28 swollen joint count, CRP and subject assessment of disease activity measure on a visual analogue scale (VAS) of 100mm. The formula for calculation of DAS28-CRP is given below:

$$\text{DAS28-CRP} = 0.56 * \text{sqrt}(\text{tender28}) + 0.28 * \text{sqrt}(\text{swollen28}) + 0.36 * \ln(\text{hsCRP}+1) + 0.014 * \text{VAS} + 0.96.$$

The measurement of hsCRP should be in mg/L. If any component is missing, then DAS28-CRP will not be calculated.

8.1.5 Schirmer's Test

Schirmer's test will be performed as described in protocol Section 5.4.3. The CRF collects the length in millimeters that the strip wets during the 5 minute test period for each eye. Collection is done separately for each eye.

8.1.6 Tear Break-up Time

Tear break up time will be assessed as described in protocol Section 5.4.3. The CRF collects the time in seconds to first appearance of a random dry spot on the corneal surface for 3 repetitions in each eye. The average time will be calculated for each eye averaging the 3 measurements for each eye separately. In case only 2 measurements are available, the average of the 2 measurements will be calculated. In case there is only 1 measurement, that measurement will be used for the analysis.

8.1.7 Ocular Surface Staining

Ocular surface staining will be assessed as described in protocol Section 5.4.3. The CRF collects the score for the following for each eye:

- MNBC (Medial Nasal Bulbar Conjunctiva) [maximum score = 3],
- CORN (Corneal Staining of Punctate Epithelial Erosions (PEE)) [maximum score = 3],
- LTBC (Lateral Temporal Bulbar Conjunctiva) [maximum score = 3],
- CONF (Patches of Confluent Staining) [maximum score = 1],

- PUGL (PEE observed in the pupil region, i.e. central 4mm diameter portion of the cornea) [maximum score = 1],
- FILA (one of more filaments seen anywhere on the cornea) [maximum score = 1]

The total score will be calculated as the sum of the score for these parameters for each eye.

8.1.8 Numeric Rating Scale (NRS) Scores

The oral and ocular dryness are each assessed by the patients with numeric rating scales from 0 to 10 with 0 representing no dryness and 10 representing maximal dryness (protocol Appendices 8 and 9). The analysis will be based on the scores as reported on the CRF.

8.1.9 Visual Analog Scale

The subject and physician global assessment of disease activity are assessed with visual analog scales presented in protocol Appendices 4 and 5. The CRF collects the distance in millimeters from the start of the scale that is marked as well as the length of the scale in millimeters. In cases that the length of the scale is in less or more than 100 millimeters, then the subject's or physician measurement will be rescaled to the equivalent of 100 millimeters using the formula below:

Figure 8.1.9-1: Formula to Rescale Visual Analog Scale

$$\text{Rescale measurement in mm} = \frac{\text{measurement as reported on CRF in mm}}{\text{length of the line on CRF in mm}} \cdot 100 \text{ mm}$$

8.1.10 Short Form-36 (SF-36 v2.0)

The SF-36 v2.0 is composed of 36 items (questions) measuring 8 health concepts (scales): Physical Function, Role-Physical, Bodily Pain, General Health, Vitality, Social Functioning, Role-Emotional, and Mental Health. The 8 scales are used to form two summary scales: Physical Component Summary (PCS) and Mental Component Summary (MCS).

The QualityMetric Health Outcomes Scoring Software 5.0 will be used for scoring these scales

8.1.11 Female Sexual Function Index (FSFI)

For the FSFI, domain scores are calculated by summing the scores of the individual questions that make up the domain and multiplying the sum by the factor in the table below. The full scale score is the sum of the six domain scores.

For subjects without a partner, thus not able to answer item 15, the domain score for satisfaction and the full scale score will not be calculated.

Table 8.1.11-1: Scoring Algorithm for Female Sexual Function Index (FSFI)

Domain	Questions	Score Range	Factor	Minimum score	Maximum score
Desire	1, 2	1–5	0.6	1.2	6.0
Arousal	3, 4, 5, 6	0–5	0.3	0	6.0
Lubrication	7, 8, 9, 10	0–5	0.3	0	6.0
Orgasm	11, 12, 13	0–5	0.4	0	6.0
Satisfaction	14, 15, 16	0 (or 1)–5	0.4	0	6.0
Pain	17, 18, 19	0–5	0.4	0	6.0
Full Scale Score Range				2.0	36.0

8.1.12 PROMIS Fatigue Short Form 8a

As mentioned in the brief guide to the PROMIS Fatigue instruments “each question has five response options ranging in value from one to five ... To find the total raw score for a short form with all questions answered, sum the values of the response to each question. For example, for the 8-item form, the lowest possible raw score is 8; the highest possible raw score is 40”. Table 8.1.12-1 presents the raw score values.

“A score can be approximated if a participant skips a question. If items are missing, first check how many items were answered. For short forms with at least 5 items, confirm that 4 or 50% of items, whichever is greater, were answered.” If less than 4 items were answered, then the T-score cannot be calculated “After confirming that enough responses were provided, sum the response scores from the items that were answered (not including any screening question). Multiply this sum by the total number of items in the short form. Finally, divide by the number of items that were answered. For example, if a respondent answered 5 of 8 questions and answered all items with the second lowest response option (2), you would sum all responses (10), multiply by the number of items in the short form (8) and divide by the number of items that were answered (5). Here $(10 \times 8) / 5 = 16$. If the result is a fraction, round up to the nearest whole number. This is a pro-rated raw score. Again, the formula is:

[figure not shown]
Figure 8.1.12-1: Formula for PROMIS Raw Score

$$\frac{(\text{Raw sum} \times \text{number of items on the short form})}{\text{Number of items that were actually answered}}$$

Locate the applicable score conversion table in ... [Table 8.1.12-1] and use this table to translate the total raw score or pro-rated score into a T-score for each participant. The T-score rescales the raw score into a standardized score with a mean of 50 and a standard deviation (SD) of 10.... The standardized T-score is reported as the final score for each participant. ... For pro-rated

scores, this calculation assumes that responses are missing at random. This isn't always true. Therefore, use caution when interpreting the final pro-rated T-score."

The PROMIS brief guide refers to the calculation of 95% confidence intervals for subject's scores. Only the T-score will be used for every subject for the analyses described in this analysis plan.

